8.2 Sample size determination

A previous study by Rush investigators observed folate deficiency (<7 ng/mL) in 66% of patients treated with olaparib. A sample size of $n=60$ is calculated using one-sided test to have 80% power in detecting more than half (50%) of the patients having folate deficiency at 0.05 significance level. Allowing for 20% attrition, we propose a sample size of $n=75$ for this study.

8.3 Populations for analyses

Clinical Study Protocol - 6
Olaparib - ESR-18-13807

All enrolled patients who receive at least one dose of olaparib will be included in the analysis population to be used to assess the efficacy and safety endpoints.

8.4 Statistical analyses

8.4.1 Efficacy analyses

Patients will be monitored for development of anemia and folate deficiency at scheduled time points throughout the course of the study, as described in Section 1.1. Patients who develop \leq G2 cytopenias and folate deficiency will be randomly assigned in a 1:1 ratio to receive folic acid supplementation 1 mg daily or no supplementation. Patients who develop G3 or higher cytopenias and folate deficiency will be started on folic acid supplementation, thus not included in the randomization. For patients who are randomized, we will assess the impact of folic acid supplementation on anemia, need for transfusion, and dose interruption, dose reduction and drug discontinuation of olaparib as compared to those who did not receive/require folic acid supplementation. Additionally, PFS and RR to olaparib will be compared amongst randomized patients relative to folic acid supplementation.

The statistical analysis will provide descriptive summaries as well as 95% confidence intervals for the primary endpoint of drug-induced folate deficiency in addition to response rate and other secondary endpoints. Kaplan-Meier methodology will be used to estimate the PFS curve and estimate of median PFS and corresponding 95% confidence interval will be provided. The significance of the observed percentage of folate-deficient cases will be assessed by statistical hypothesis test, as well as by multivariable analysis of the binary endpoint of folate deficiency adjusted by important covariates. Covariates will include age, race/ethnic group, previous therapy, Hgb prior to olaparib therapy, genetic testing result (*BRCA* carrier status). RR and PFS will be compared to historical controls as a descriptive comparison. Analyses will be reported on the entire combined cohort of patients with solid tumors and also separately for each cancer type. The statistical analysis of the exploratory endpoint will be specified in the SAP. Statistical analysis will be performed in the R Statistical software. No adjustment for multiplicity will be made.

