1. PROTOCOL SUMMARY

1.1 Schedule of Activities (SoA)

1. Participants will be screened for eligibility with medical history, physical exam, prior treatment, history of anemia and blood tests including baseline CBC, reticulocyte count, ferritin, B-12 and serum folate level
2. If inclusion criteria are met and after signing a consent form, participants will start olaparib 300 mg twice daily, commercially approved
3. Assessment of CBC/serum folate will occur every 2 weeks for the first 3 months and then monthly for a total of 6 months from the time of enrollment onto study therapy. If the patient develops folate deficiency and requires folate replacement, CBC/serum folate and reticulocyte count will occur every 2 weeks for 12 months.
4. One-time measurement of serum folate to occur one month after completion or discontinuation of therapy with olaparib
5. If folate deficiency is identified (defined as any level below normal) at any time point, the following parameters will be assessed in 2 weeks or at the next visit/assessment point: a repeat CBC/serum folate level along with B-12, LDH, reticulocyte count, methylmalonic acid, and homocysteine. These labs (CBC/serum folate level, B-12, LDH, reticulocyte count, methylmalonic acid, and homocysteine) need to be drawn once- 2 weeks after initial folate deficiency is identified for confirmation purposes and to rule out co-existing B-12 deficiency or other causes of anemia.
6. Once folate deficiency is confirmed in the setting of hemoglobin (Hgb) less than 12 g/dl but above 10.0 g/dl, patients will be randomized to folate supplementation or placebo. At that point, assessment of CBC/reticulocyte count and folate levels will continue every 2 weeks.
7. If Hgb is above 12.0 g/dl and no folate deficiency is identified, patients will not be randomized. Assessment of CBC/serum folate will continue every 2 weeks for the first 3 months and then monthly for a total of 6 months from the time of enrollment onto the study.
8. If folate deficiency is identified in setting of Hgb less than 10.0 g/dl, patients will not be randomized but will receive folic acid supplementation at 1 mg daily. These patients will have weekly assessments of CBC/reticulocyte count and folate levels until Hgb improves to a level above 10.0 g/dl. At that point, assessment of CBC/reticulocyte count and folate levels will change back to every 2 weeks. However, folic acid replacement will continue as initiated.

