3. STUDY DESIGN

3.1 Overall design

This is a pilot, multi-center study evaluating the prevalence and timing of folate deficiency in patients with advanced solid tumors who are eligible to receive olaparib.

If patients develop folate deficiency concomitantly with a Hgb less than 12.0 g/dl (grade 1), they will then be randomized to receive either a placebo or folate supplementation.

All randomized patients who develop a Hgb less than 10 g/dl (grade 2) concomitantly with folate deficiency will receive folic acid supplementation irrespective of their prior randomization. If such patients were originally randomized to receive folic acid and continue to have a Hgb less than 10 g/dl and folate deficiency despite folate supplementation, folic acid dose will be increased to 2 mg daily or higher at the discretion of the investigator.

Patients will continue with olaparib until objective disease progression (determined by treating physician assessment) as long as in the Investigator's opinion they are benefiting from treatment and they do not meet any other discontinuation criteria.

For an overview of the study design see Figure 1, Section 1.3. For details on treatments given during the study, see Section 5.1 Treatments Administered.

For details on what is included in the efficacy and safety endpoints, see Section 2 Objectives and Endpoints.

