7.4.4.1 Management of haematological toxicity

7.4.4.2 Management of anaemia

Table 8 Management of anaemia

Haemoglobin	Action to be taken
Hgb < 10 but ≥ 8 g/dl (CTCAE Grade 2)	
First occurrence: Give appropriate supportive treatment and investigate causality. Investigator judgement to continue olaparib with supportive treatment (e.g., transfusion) or interrupt dose for a maximum of 4 weeks. Study treatment can be restarted if Hb has recovered to > 9g/dl.
 
Subsequent occurrences: If Hgb < 10 but ≥ 9 g/dl investigator judgement to continue olaparib with supportive treatment (e.g., transfusion) or dose interrupt (for max of 4 weeks) and upon recovery dose reduction may be considered (to 250 mg twice daily as a first step and to 200 mg twice daily as a second step). If Hgb < 9 but ≥ 8 g/dl, dose interrupt (for max of 4 weeks) until Hb ≥ 9 g/dl and upon recovery dose reduction may be considered (to 250 mg twice daily as a first step and to 200 mg twice daily as a second step).

Hgb < 8 g/dl (CTCAE Grade 3)	
Give appropriate supportive treatment (e.g., transfusion) and investigate causality. Interrupt olaparib for a maximum of 4 weeks until improved to Hgb ≥ 9 g/dl. Upon recovery dose reduce to 250 mg twice daily as a first step and to 200 mg twice daily as a second step in the case of repeat Hgb decrease.

Common treatable causes of anemia (e.g., iron, vitamin B12 or folate deficiencies and hypothyroidism) should be investigated and appropriately managed. In some cases management of anemia may require blood transfusions. For cases where patients develop prolonged haematological toxicity (≥2 week interruption/delay in study treatment due to CTC grade 3 (Hgb less than 8.0 g/dl) or worse anemia and/or development of blood transfusion dependence), refer to guidance later in this section for the management of this.

Clinical Study Protocol - 6
Olaparib - ESR-18-13807

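### Section 8.4.1 randomises folate-deficient patients with Hgb 8 to <10 g/dl, whereas Section 1.1 item 8 withholds randomisation and gives them folic acid

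*Combined protocol and SAP*

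**What the plan says.** Section 8.4.1 sets allocation by cytopenia grade. Patients with at most "G2 cytopenias and folate deficiency will be randomly assigned in a 1:1 ratio to receive folic acid supplementation 1 mg daily or no supplementation". The next sentence names those left out: "Patients who develop G3 or higher cytopenias and folate deficiency will be started on folic acid supplementation, thus not included in the randomization".

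Section 1.1 sets allocation by haemoglobin. Item 6 reads: "Once folate deficiency is confirmed in the setting of hemoglobin (Hgb) less than 12 g/dl but above 10.0 g/dl, patients will be randomized". The two arms named there are folate and placebo. Item 8 reads: "If folate deficiency is identified in setting of Hgb less than 10.0 g/dl, patients will not be randomized but will receive folic acid supplementation". The dose in that item is 1 mg daily.

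Table 8 in Section 7.4.4.2 supplies the protocol's own link between grade and haemoglobin. Its two rows are labelled "Hgb < 10 but ≥ 8 g/dl (CTCAE Grade 2") and "Hgb < 8 g/dl (CTCAE Grade 3").

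Section 3.1 combines the two scales: "If patients develop folate deficiency concomitantly with a Hgb less than 12.0 g/dl (grade 1), they will then be randomized". It then labels Hgb below 10 g/dl as grade 2 and gives folic acid to any randomised, deficient patient who reaches that level, whichever arm they were in. Section 5.6 uses the same grade 2 label for Hgb below 10 g/dl.

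**The concern.** Eligibility for randomisation should have one rule. Here the section that governs the analysis and the section that governs treatment give opposite instructions for the same patient: folate-deficient, with Hgb from 8 to just under 10 g/dl.

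Two things are at stake.

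- **Care.** A site that follows 8.4.1 could assign such a patient to no supplementation, although item 8 requires folic acid. Section 7.4.4.2 also asks that treatable causes of anaemia, folate deficiency among them, be managed.
- **Analysis.** If the site then applies 3.1, a control randomised in this band may qualify for folic acid at or soon after randomisation and contributes little contrast. The comparisons exposed are the randomised secondary ones: anaemia, transfusion, olaparib interruption, reduction and discontinuation, response rate (RR) and progression-free survival (PFS).

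The study is multi-centre, so different sites could apply different rules.

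**Working it through.** **1. The plan's own figure.** The inputs, from Section 8.2, are a 50% null rate, a 66% expected rate, a one-sided 0.05 level, 80% power and 20% attrition.

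- Normal approximation: n = [(1.645 × √(0.5 × 0.5) + 0.842 × √(0.66 × 0.34)) / 0.16]² = 58.2, rounded up to 59.
- Exact binomial at n = 60, rejecting at 37 or more deficient patients: one-sided alpha 0.046, power 0.802.
- Attrition: 60 / (1 − 0.20) = 75.

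Both 60 and 75 reproduce. They rest on the rate of deficiency and not on who is later randomised, so neither allocation rule changes them.

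**2. The two rules side by side.** The Table 8 bands translate the 8.4.1 grades into haemoglobin. Section 3.1 supplies the grade 1 label below 12.0 g/dl. All patients in the table are folate-deficient, and anaemia is their only cytopenia.

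| Hgb (g/dl) | Grade | Section 8.4.1 | Section 1.1 | Agree? |
|---|---|---|---|---|
| 11 | 1 | randomise | randomise (item 6) | yes |
| 9.9 | 2 | randomise | folic acid, not randomised (item 8) | no |
| 9.0 | 2 | randomise | folic acid, not randomised (item 8) | no |
| 8.0 | 2 | randomise | folic acid, not randomised (item 8) | no |
| 7.9 | 3 | folic acid, not randomised | folic acid, not randomised (item 8) | yes |

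Below 10 g/dl, the conflict is exactly the band from 8 to <10.

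**3. Which section is out of line.** The conflict is not a difference in grade numbering, because Table 8, 3.1 and 5.6 all call Hgb below 10 g/dl grade 2. Items 6 and 8 of 1.1, the column split in 1.1.1 B, the footnote to Figure 1, the folic acid rule in 3.1 and the dose rule in 5.6 all turn on 10 g/dl. Only 8.4.1 moves the line to grade 3, that is, to 8 g/dl. The randomisation sentence in 3.1 has no lower bound, so it does not settle the matter alone, but its grade 1 label fits item 6. Section 5.3, on randomisation and blinding, states no eligibility rule.

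**4. The boundary.** Hgb of exactly 10.0 g/dl falls under neither item 6 (above 10.0) nor item 8 (below 10.0).

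**The case against.** The strongest reply is that sites work from the schedule and the design section, which all use 10 g/dl. Section 8.4.1 itself points to Section 1.1 for monitoring. On that view nobody is misallocated and one sentence in the statistics section is wrong. Much of this stands: it is the likelier course, and it limits the consequence. It does not remove the contradiction, because no section says which rule prevails.

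A reader might infer a size for the damage. At the planning rate, 0.66 × 60 = 39.6 deficient patients, or 19.8 controls at 1:1. If 10% to 40% of them were in the disputed band, 2.0 to 7.9 controls would be affected. The documents do not support this:

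- The 10% to 40% share has no source.
- About 20 controls is a ceiling that neither rule reaches. Section 1.1 also requires Hgb below 12 g/dl; 8.4.1 also requires a cytopenia and excludes grade 3 or higher.
- If sites follow 1.1, the number of controls affected by the 8.4.1 wording is zero.

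A reader might also infer that the comparison is free of dilution if 1.1 is followed. It is not: 3.1 gives folic acid to deficient controls who later fall below 10 g/dl under either entry rule. Nor does 3.1 plainly trigger at the moment of randomisation, since it speaks of patients who develop the low value. Hence the qualification *at or soon after*.

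Finally, the word *cytopenias* could be taken to bring in patients with neutropenia alone. The sentence just before it in 8.4.1 concerns anaemia and folate deficiency, so that reading should not be pressed.

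**Conclusion.** The contradiction is real and follows from the protocol's own grade table. As written, 8.4.1 randomises deficient patients with Hgb 8 to <10 g/dl, and 1.1 item 8 does not. Section 8.4.1 is the outlier.

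The consequence depends on which rule sites apply:

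- **Under 8.4.1**, some patients could be left without folic acid that item 8 requires, or could dilute the randomised secondary comparisons through early rescue.
- **Under 1.1**, allocation is right and 8.4.1 merely misdescribes the randomised group.

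How many patients this touches cannot be computed from the documents. The primary endpoint and n=60/75 are unaffected, and the study is a pilot. The point should be fixed because it decides who is randomised and who is treated, but it does not undermine the main result.

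**What to change.** First, the sponsor confirms that 10 g/dl is the intended cut-off. Then replace the two allocation sentences in 8.4.1 with:

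> Patients with confirmed folate deficiency (as defined in Section 1.1) and Hgb >=10.0 and <12.0 g/dl will be randomised 1:1 to folic acid 1 mg daily or the control described in Sections 1.1 and 3.1 (placebo). Patients not yet randomised who have folate deficiency and Hgb <10.0 g/dl will not be randomised and will receive folic acid 1 mg daily.

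Add the 10.0 g/dl lower bound to the randomisation sentence in 3.1. Use *10.0 or above* in 1.1 items 6, 8 and 9 and in the biweekly column of 1.1.1 B. All four places must change together; otherwise a patient at exactly 10.0 g/dl would be on weekly testing in one place and two-weekly in another.

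The wording refers to Section 1.1 for the definition of deficiency on purpose. Item 5 there uses any level below normal, while the primary endpoint uses <7 ng/mL, and this change should not settle that question unnoticed.

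The cost is amendment text in 8.4.1, 3.1, 1.1 and 1.1.1 B. Sample size and the set of laboratory tests stay as they are; testing frequency is clarified only at exactly 10.0 g/dl.

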2. OBJECTIVES AND ENDPOINTS

Primary objective:

To determine the frequency and timing of folate deficiency in patients with solid tumors harboring molecular alterations such as germline and somatic mutations in *BRCA1* and *BRCA2* genes, other genes in Homologous DNA Recombination Repair (HRR) pathway, genomic stability as determined by Homologous Recombination Deficiency (HRD) assay, etc., who are treated with olaparib.

Secondary objectives:

To evaluate the effect of folic acid supplementation on serum folate, hemoglobin level, transfusion needs/number of transfusions, and need for olaparib treatment interruption, dose reduction and drug discontinuation.

To assess response rate (RR) to olaparib as it relates to serum folate level and folic acid supplementation.

Clinical Study Protocol - 6
Olaparib - ESR-18-13807

To assess progression-free survival (PFS) as it relates to serum folate level and folic acid supplementation.

Exploratory objectives:

To elucidate the mechanism of folate deficiency in patients treated with olaparib including possible interaction with germline *BRCA1* and *BRCA2* mutations via testing for folate receptors using immunohistochemistry on available paraffin embedded tumor samples from enrolled patients.

Primary endpoint:

The primary binary endpoint of the study is the percentage of patients who develop drug-induced folate deficiency, defined as serum folate level <7 ng/mL, within three months from start of olaparib therapy.

Secondary endpoints:

To assess the impact of folic acid supplementation on anemia, need for transfusion, and olaparib treatment interruption, dose reduction and drug discontinuation as compared to those who did not receive/require folic acid supplementation

To determine tumor response rate (RR), using treating physician assessment, on olaparib therapy in patients who develop folate deficiency and receive folic acid supplementation as compared to those who do not receive/require folic acid supplementation. Will also compare RR to historical controls (patients with solid tumors treated with olaparib or other approved agents on clinical trials).

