To determine progression-free survival (PFS), using treating physician assessment based on olaparib therapy in patients who develop folate deficiency and receive folic acid supplementation as compared to those who do not receive/require folic acid supplementation. Will also compare PFS to historical controls (patients with solid tumors treated with olaparib or other approved agents on clinical trials) using published data.

Exploratory Endpoints:

To evaluate association between:

- *BRCA 1*, *BRCA 2*, and other HRR gene status (germline mutation carrier vs non-carrier) and the intensity of folate receptor alpha expression in the tumor ($<50\%$ or $>50\%$)
- *BRCA 1*, *BRCA 2*, and other HRR gene status (germline mutation carrier vs non-carrier) and nadir serum folate level during olaparib treatment

Clinical Study Protocol - 6
Olaparib - ESR-18-13807

- *BRCA 1*, *BRCA 2*, and other HRR gene status (germline mutation carrier vs non-carrier) and tumor response in patients receiving folate supplementation as compared to patients not receiving folate supplementation and historical controls
- Folate deficiency and expression of folate receptors in patients' tumor samples

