4.2 Exclusion criteria

Medical conditions

1. Patients with folic acid deficiency, defined as folate <7 ng/mL, or those taking folic acid supplementation within 30 days of olaparib initiation.
2. Other malignancy unless curatively treated with no evidence of disease for ≥ 5 years except: adequately treated non-melanoma skin cancer, curatively treated in situ cancer of the cervix, ductal carcinoma in situ (DCIS), Stage 1, grade 1 endometrial carcinoma. Patients with a history of localised triple negative breast cancer may be eligible, provided they completed their adjuvant chemotherapy more than three years prior to registration, and that the patient remains free of recurrent or metastatic disease
3. Persistent toxicities (>Common Terminology Criteria for Adverse Event (CTCAE) grade 2) caused by previous cancer therapy, excluding alopecia.
4. Patients with myelodysplastic syndrome/acute myeloid leukaemia or with features suggestive of MDS/AML.

Clinical Study Protocol - 6
Olaparib - ESR-18-13807

5. Patients with symptomatic uncontrolled brain metastases. A scan to confirm the absence of brain metastases is not required. The patient can receive a stable dose of corticosteroids before and during the study as long as these were started at least 4 weeks prior to treatment. Patients with spinal cord compression unless considered to have received definitive treatment for this and evidence of clinically stable disease for 28 days.
6. Patients considered a poor medical risk due to a serious, uncontrolled medical disorder, non-malignant systemic disease or active, uncontrolled infection. Examples include, but are not limited to, uncontrolled ventricular arrhythmia, recent (within 3 months) myocardial infarction, uncontrolled major seizure disorder, unstable spinal cord compression, superior vena cava syndrome, extensive interstitial bilateral lung disease on High Resolution Computed Tomography (HRCT) scan or any psychiatric disorder that prohibits obtaining informed consent.
7. Patients unable to swallow orally administered medication and patients with gastrointestinal disorders likely to interfere with absorption of the study medication.
8. Immunocompromised patients, e.g., patients who are known to be serologically positive for human immunodeficiency virus (HIV).
9. Patients with known active hepatitis (i.e. Hepatitis B or C).

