5.5 Concomitant therapy

The use of any natural/herbal products or other traditional remedies should be discouraged, but use of these products, as well as any medication or vaccine including over-the-counter or prescription medicines, vitamins, and/or herbal supplements that the patient is receiving at the time of enrolment or receives during the study must be recorded along with:

- Reason for use
- Dates of administration including start and end dates
- Dosage information including dose and frequency

The information on vitamin intake will be collected at the baseline and throughout the duration of the study. Patients will be discouraged to take folate-containing vitamin supplements for at least three months after starting olaparib therapy. However, if they have been on them before the enrolment and decline holding them, they are still eligible to participate.

Anti-emetics/Anti-diarrheals

From screening onwards, should a patient develop nausea, vomiting and / or diarrhea, then these symptoms should be reported as AEs (see Section 8.3) and appropriate treatment of the event given.

Medications that may NOT be administered

Table 2 Prohibited medications

Prohibited medication/class of drug:	
Anticancer therapy:	Not permitted while the patient is receiving study medication
Chemotherapy	
Immunotherapy	
Radiotherapy (except palliative)	
Biological therapy	
Other novel agents	

*Hormone Replacement Therapy (HRT) is acceptable

Clinical Study Protocol - 6
 Olaparib - ESR-18-13807

*Anti-hormonal agents such as aromatase inhibitors are acceptable.

Restricted concomitant medications

Table 3 Restricted concomitant medications

Medication/class of drug:	Usage (including limits for duration permitted and special situations in which it’s allowed):

Strong CYP3A inhibitors:
 
itraconazole, telithromycin, clarithromycin, boosted protease inhibitors, indinavir, saquinavir, nelfinavir, boceprevir, telaprevir
	
Strong or moderate CYP3A inhibitors should not be taken with olaparib. If there is no suitable alternative concomitant medication then the dose of olaparib should be reduced for the period of concomitant administration. The dose reduction of olaparib should be recorded in the CRF with the reason documented as concomitant CYP3A inhibitor use.

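### The multivariable model of folate deficiency adjusts for haemoglobin before olaparib but not for serum folate before olaparib, although folate is measured in every patient at screening

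*Combined protocol and SAP*

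**What the plan says.** Section 2 defines the primary endpoint as the percentage of patients who develop drug-induced folate deficiency, "defined as serum folate level <7 ng/mL, within three months from start of olaparib therapy".

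Section 8.4.1 gives this endpoint a descriptive summary, a 95% confidence interval and a hypothesis test, "as well as by multivariable analysis of the binary endpoint of folate deficiency adjusted by important covariates". The adjustment set follows: "Covariates will include age, race/ethnic group, previous therapy, Hgb prior to olaparib therapy, genetic testing result", the last being BRCA carrier status. That makes five covariates. Haemoglobin before treatment is one of them and folate before treatment is not.

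Folate before treatment is available. Section 1.1, item 1, has every participant screened with "blood tests including baseline CBC, reticulocyte count, ferritin, B-12 and serum folate level", and the Folate row of table 1.1.1 A marks the screening visit. The stated use of that value is eligibility. Section 4.2 excludes "Patients with folic acid deficiency, defined as folate <7 ng/mL, or those taking folic acid supplementation within 30 days of olaparib initiation". No upper limit is set. Section 5.5 says of patients already on folate-containing vitamins that "if they have been on them before the enrolment and decline holding them, they are still eligible to participate".

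No other section adds baseline folate to this model. Section 8.4.1 defers only the exploratory endpoint analysis to the SAP. One exploratory endpoint in Section 2 relates mutation status to "nadir serum folate level during olaparib treatment".

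**The concern.** The outcome is a continuous laboratory value cut at 7 ng/mL, and eligibility uses the same value and the same cut. A patient who enters just above the cut needs a small fall to become a case, while one who enters well above it needs a large fall. The model adjusts for the baseline of a different measurement and leaves out the baseline of the outcome.

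Two consequences follow for the adjusted associations. First, if prior therapy, race/ethnic group, haemoglobin or BRCA status is related to starting folate, that relation passes into its odds ratio. A marker of starting low could then be read as a marker of losing folate on olaparib, which matters because the endpoint is described as drug-induced. Second, a covariate that really does affect folate loss can show a smaller odds ratio than it has among patients with the same starting value.

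**Working it through.** **1. The plan's own figure.** Inputs from Section 8.2: null 50%, expected 66% ("A previous study by Rush investigators observed folate deficiency (<7 ng/mL) in 66% of patients treated with olaparib"), one-sided alpha 0.05, power 80%.

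n = [(1.645·√(0.5·0.5) + 0.842·√(0.66·0.34)) / 0.16]² = 58.2, so 59.

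Exact binomial at n=60: reject at 37 or more cases, alpha 0.0462, power 0.802. Attrition: 60/(1 − 0.20) = 75. Both stated figures reproduce. They rest on the one-sample test, which uses no covariates, so the covariate list cannot change them.

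**2. How far a patient must fall.** Fall needed = (baseline − 7)/baseline. From 7.5 ng/mL: 0.5/7.5 = 6.7%. From 15 ng/mL: 8/15 = 53.3%. The eligibility floor truncates baseline folate but does not make it constant.

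**3. Can omission create a false risk factor?** The documents give no folate distribution, so these inputs are assumptions:
- baseline folate is log-normal, with geometric mean 11 ng/mL before truncation at 7;
- a binary covariate (half of patients before truncation) lowers that geometric mean by 20% and has no effect on the fall;
- the log fall is normal, with its mean set so that 66% end below 7.

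Large-sample logistic odds ratios for the covariate (400,000 simulated patients per setting):

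| log-SD baseline | log-SD fall | without baseline folate | with log baseline folate |
|---|---|---|---|
| 0.3 | 0.2 | 2.29 | 0.99 |
| 0.3 | 0.3 | 1.96 | 0.99 |
| 0.3 | 0.4 | 1.75 | 1.02 |
| 0.4 | 0.2 | 1.88 | 0.99 |
| 0.4 | 0.3 | 1.71 | 1.00 |
| 0.4 | 0.4 | 1.57 | 1.00 |
| 0.5 | 0.2 | 1.68 | 0.99 |
| 0.5 | 0.3 | 1.57 | 1.00 |
| 0.5 | 0.4 | 1.47 | 0.99 |

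The middle setting gives about 1.7, and the range is 1.5 to 2.3. The true value is 1, and the added term recovers it.

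For scale at the trial's size, the standard error of a log odds ratio for an evenly split binary covariate is roughly √[4/(n·0.66·0.34)]: 0.55 at n=60 and 0.49 at n=75. Since log 1.7 = 0.53, the bias is about one standard error.

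**4. Can omission hide a real association?** A second set of assumptions: median 12 ng/mL before truncation, log-SD 0.45, 66% cases, a modest true BRCA effect independent of baseline, and a null haemoglobin effect.

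| Correlation, baseline vs on-treatment | AUC without | AUC with | BRCA odds ratio without | with |
|---|---|---|---|---|
| 0 | 0.56 | 0.56 | 1.63 | 1.63 |
| 0.3 | 0.56 | 0.65 | 1.59 | 1.64 |
| 0.5 | 0.56 | 0.75 | 1.61 | 1.77 |
| 0.7 | 0.56 | 0.85 | 1.62 | 2.09 |

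The loss is nil at zero correlation and grows with it. BRCA is independent of baseline here, so the gap between the last two columns is the usual difference between a marginal and a conditional odds ratio. The figure without baseline is too small as an answer about patients with equal starting folate.

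**5. Cost in the model.** Count one parameter per listed covariate, so five now and six after the change. Smaller outcome class = n × min(p, 1 − p).

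| n | event rate | smaller class | per parameter, 5 | per parameter, 6 |
|---|---|---|---|---|
| 60 | 66% | 20.4 | 4.1 | 3.4 |
| 75 | 66% | 25.5 | 5.1 | 4.2 |
| 60 | 50% | 30 | 6.0 | 5.0 |
| 75 | 50% | 37.5 | 7.5 | 6.2 |

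Race/ethnic group and previous therapy may each need more than one parameter, so these are upper figures.

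**The case against.** The strongest reply is about scope. The plan does not call this model primary. The endpoint is a percentage, the trial is sized on a one-sample test, and the adjusted analysis stands beside that test. A reader might infer that the primary result is biased. The documents do not support that, because the percentage, its interval and its test use no covariates.

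Four further replies have weight:

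- **Strength of the predictor.** A reader might infer that baseline folate is the strongest predictor available. No figure in the documents shows this. It is a reasonable expectation for the baseline of the outcome, and the size of the problem depends on a correlation the documents do not give.
- **A different question.** If prior therapy lowers starting folate, its association without baseline adjustment still describes who becomes deficient. That is a legitimate question, but it is not the one the term drug-induced points to.
- **Wording of the list.** It can be read as non-exhaustive. Leaving this covariate to be chosen after the data are seen is a reason to name it now.
- **Thin model.** This stands in full. A sixth term costs something, and results by cancer type are also planned.

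A reader might also infer that the nadir-folate comparison is planned without baseline adjustment. The documents do not say so: that analysis is deferred to the SAP. For the same reason, a gain in effective sample size computed for continuous nadir folate should not be carried over to the binary model. In two assumed settings (log-SD of baseline and fall 0.3/0.4 and 0.4/0.3), with a baseline-independent covariate shifting log folate by 0.15, the squared z-ratio gain in the logistic model was about 1.2 and 1.65.

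**Conclusion.** The omission is real and confined to the adjusted analysis in Section 8.4.1. Baseline folate is collected in everyone, varies above a floor of 7 ng/mL, and can be expected to predict the outcome well. Leaving it out could turn a covariate tied only to starting folate into an apparent risk factor (odds ratio about 1.7 under the assumed distributions, against a true value of 1), and can understate a real association.

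These sizes rest on assumed log-normal folate, a fall independent of baseline, a 20% difference in starting geometric mean and a 66% event rate. The documents do not show that any listed covariate is in fact related to starting folate, so this is a risk and not a forecast. If baseline and on-treatment folate were uncorrelated, the omission would cost nothing.

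**What to change.** Add serum folate before olaparib to the covariate list in Section 8.4.1 as one continuous term on the log scale. No new data, visits or patients are needed, and n=60/75 stands.

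The price is one parameter, with the reduction shown in the working. If the team judges that too thin, collapsing a weaker covariate (for example, levels of race/ethnic group) or using penalised estimation would keep the new term affordable. The first option gives up detail on another prespecified covariate and should be stated in advance.

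When the SAP specifies the exploratory comparison of nadir folate by mutation status, it should include the same baseline term.
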